12. Any use of light-activated medications (photodynamic therapy) within 14 days prior to study enrollment (in the U.S .Visudin (verteporfin) - for age-related macular degeneration; Aminolevulinic acid - for actinic keratoses; Photofrin (sodium porfimer) - for esophageal cancer, non-small cell lung cancer; Levulan Kerastick (aminolevulinic acid HCl) - for actinic keratoses; 5-aminolevulinic acid (ALA) - for nonmelanoma skin cancer)
13. Recent history of stroke (90 days).
14. Subject had a failed intervention based on an FDA-approved device for the treatment of depression, during the current episode (e.g., less than 50% decrease in depressive symptomatology with TMS, ECT, or VNS).
15. History of dementia, traumatic brain injury (TBI) or other organic neurological disorder.

Near Infrared Transcranial Laser Therapy in Subjects with Major Depressive Disorder: A study of Dosing with Laser.

2. List of Abbreviations

ANCOVA = Analysis of Covariance
ANOVA = Analysis of Variance
ASQ = Anxiety Symptom Questionnaire
ATP = Adenosine Triphosphate
BOLD fMRI = blood-oxygen level dependent functional magnetic resonance imaging
C-SSRS = Columbia Suicide Severity Rating Scale
CFR = Code of Federal Regulations
CGI-I = Clinical Global Impressions: Improvement
CGI-S = Clinical Global Impressions: Severity
CRF= Case Report Form
CW = Continuous Wave
DNA = Deoxyribonucleic acid
DSMB = Data and Safety Monitoring Board
ECT= Electroconvulsive Therapy
ETC= Electron Transport Chain
FDA= Food and Drug Administration
HAM-D-17 = Hamilton Depression Rating Scale
HCTZ = Hydrochlorothiazide
ISO = International Standards Organization
MDD = Major depressive disorder
MINI= Mini-International Neuropsychiatric Interview
NEST 1 = NTS® Effectiveness and Safety Trial - 1
NEST 2 = NTS® Effectiveness and Safety Trial - 2
NIMH = National Institute of Mental Health
NIR-TLT = Near-infrared Transcranial Laser Therapy
OSHA = Occupational Safety & Health Administration
PBM = Photobiomodulation
PET *scan* / PET: Positron Emission Tomography
PI = Principal Investigator at the center
QIDS-CR = Quick Inventory of Depressive Symptomatology: Doctor-rated scale
RA = Research associate
SAE = Serious Adverse Events
SAFTEE-SI = Systematic Assessment for Treatment Emergent Effects
SCID = Structured Clinical Interview for DSM disorders
SQL = Structured Query Language
SSRI = Selective serotonin reuptake inhibitor
t-PBM = Transcranial photobiomodulation
TLT = Transcranial Laser Therapy

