4.9 Study Visits

The study includes screening tests, treatment and a series of follow-up visits.

4.9.1 Selection Visit - Week 0

Purpose

The purpose of the screening visit will be to determine the eligibility of patients to participate in the study.

Procedures

Study personnel will consent subjects to the study, perform a psychiatric evaluation, and screen for the presence of MDD using the MINI, QIDS-C, and CGI-S scales.

Laboratory tests (including urine collection for urine biochemical analysis and urine toxin analysis (also called Urine Drug Screen), urine pregnancy test, and a complete physical examination including vital signs and weight will be performed.

Approximately 15 cc \pm 5 cc (15 ml) of blood will be drawn for laboratory safety testing. To confirm that a patient is healthy enough to participate, a complete blood work-up with differentials, thyroid stimulating hormone test, blood biochemistry (glucose, calcium, sodium, potassium, carbon dioxide, chlorine, albumin, total protein, alkaline phosphatase, transaminases, total and fractionated bilirubins, urea, creatinine) and a high sensitivity C-reactive protein test will be performed. A PET scan will be performed on patients within the study subgroup to meet the exploratory objective.

Near Infrared Transcranial Laser Therapy in Subjects with Major Depressive Disorder: A study of Dosing with Laser.

Once all tests and procedures are available for review, study personnel will determine subject eligibility based on all inclusion and exclusion criteria.

Subjects who report having taken antidepressants at the screening examination may choose to continue medication during the study or taper and discontinue therapy prior to the baseline visit (under the supervision of a treating doctor). However, subjects who have discontinued more than two antidepressants in the current episode of depression will be excluded.

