4.9.2 Treatment Visits 1 to 18 -Visits 1-6

Regular treatment visits (1 to 18) occur on non-consecutive days, 3 times per week for 6 weeks.

Purpose: The purpose of the treatment visits is to administer NIR-TLT and collect data to assess the effect of each of the NIR-TLT dose effects on MDD symptomatology (antidepressant effect) and tolerability.

Procedures: Trained study personnel will deliver NIR-TLT to study participants. Treatment visits are estimated to last approximately 429 seconds (7.15 minutes) and will take place in a dedicated NIR-TLT (laser safety) office. Only the subject and the staff administering NIR-TLT will be present during the session. The subject will lie comfortably on an examination bed or sit in a recliner, a cervical pillow (U-shaped) may be used for comfort and to prevent the helmet connector cables from being stepped on, bent or damaged. The NIR-TLT application sites (left and right forehead) will be inspected for skin lesions (e.g., lacerations or signs of inflammation) that might contraindicate treatment. During treatment sessions, a warning sign will be hung on the office door. Ideally the place where treatment is administered should be at a temperature of 25°C +/- 2°C.

Prior to treatment with the EXPi device, the subject's forehead is cleaned with 70% isopropyl alcohol, the cap is placed on the subject's head and secured, and the treatment beam locations are adjusted to match the F3 and F4 EEG sites (or very close if the site is covered by hair), the eyebrows may be used as a reference for placement of the lower edge of the helmet. The operator and subject are provided with appropriate laser safety glasses (optical density rating > 5.0 at 808 nm). Disposable caps may be used for hair control if necessary.

Trained personnel administering NIR-TLT will make every effort to never shine light into or near the subject's eyes. Patients and staff will wear safety glasses selected for the biophysical properties of NIR-TLT in accordance with Occupational Safety and Health Administration (OSHA) guidelines. The patient may sleep during the time of therapy administration.

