- **Symptoms of Depression Questionnaire (SDQ)** - This is a comprehensive measure of depression that includes assessment of symptoms on the anxiety-depression spectrum. It assesses irritability, anger outbursts, and anxiety symptoms along with symptoms commonly considered to be symptoms of depression. Factor structure analysis of the SDQ identified 5 subscales, including one on the anxiety-depression spectrum, with adequate internal consistency and concurrent validity in Spanish (Pedrelli et al., 2014).
- **Columbia Suicide Severity Rating Scale (C-SSRS)** For suicidal ideation and behavior: an FDA-endorsed instrument for clinical trials. This instrument systematically tracks suicidal ideation and behavior (e.g., suicide attempts, desire to die, suicidal thoughts, plan and intent) (Posner et al. 2007) Validated in Spanish by Al-Halabí et al.(2016).
- **Adverse Event Form**- The adverse event form captures any adverse events (serious or otherwise) specifically related to the application of TLT. This form will help determine if the side effects of TLT are too great for a participant to continue in the study.
- **Concomitant Medication Form** - This form will be completed at each TLT study visit, including the screening visit, as a safety monitoring tool.

Transcranial Near Infrared Laser Therapy in Subjects with Major Depressive Disorder: A Laser Dosing Study.

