No concomitant prohibited interventions have been reported during treatment with this device. Contraindications for use:

- Do not apply infrared light to abdominal or lumbosacral points in pregnant women.
- Do not apply infrared light to epiphyseal lines in children.
- Do not apply infrared light in the thoracic region or on the pacemaker itself in patients with pacemakers.
- Do not apply infrared light to the thyroid gland, ovaries or testicles.

Transcranial Near Infrared Laser Therapy in Subjects with Major Depressive Disorder: A Laser Dosing Study.

- Do not apply infrared light to patients who are taking
- drugs that have contraindications that are sensitive to heat or heat sensitive.
- light, such as, among others, certain types of steroids.

5. Data Analysis Methods

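### Exclusion 12 and the drug contraindication in 4.20.3 do not match, so a person can be eligible and randomised while contraindicated for the laser

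*Protocol*

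**What the plan says.** All references are to the protocol.

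- **Entry.** Exclusion 12 (section 1) bars "Any use of light-activated medications (photodynamic therapy) within 14 days prior to study enrollment". The examples that follow it are photodynamic agents. No other inclusion or exclusion criterion mentions steroids, heat-sensitive drugs or other light-sensitive drugs.
- **Who decides eligibility, and on what.** Section 4.9.1: once the screening results are in, "study personnel will determine subject eligibility based on all inclusion and exclusion criteria". It does not refer to 4.20.3.
- **Contraindication.** Section 4.20.3 contains a sentence broken over three bullets: "Do not apply infrared light to patients who are taking", then "drugs that have contraindications that are sensitive to heat or heat sensitive", then "light, such as, among others, certain types of steroids". It gives no time window.
- **Prohibited interventions.** The same section opens with "No concomitant prohibited interventions have been reported during treatment with this device".
- **Before each session.** Section 4.9.2 says the forehead sites "will be inspected for skin lesions (e.g., lacerations or signs of inflammation) that might contraindicate treatment". It also has staff collect safety data before the laser is applied, including the concomitant medication form. Section 4.10 says of that form: "This form will be completed at each TLT study visit, including the screening visit, as a safety monitoring tool".
- **Missed sessions.** Section 4.19.1 (item 8) gives a missed weekly session that cannot be made up as a reason for withdrawal. Section 4.19.2 tolerates a delay of up to 72 hours if the week's three sessions are still completed; otherwise the participant is withdrawn.

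**The concern.** The protocol has two drug rules for the same exposure, in two places, with different scope and different timing. Staff who screen work from one of them; the prohibition on applying the light sits in the other. Where they diverge, the conflict appears only after randomisation, when both ways out are poor.

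The first thing at stake is participant safety: someone whom the protocol itself says should not receive infrared light can reach the treatment room as a fully eligible participant. The second is trial conduct: if the contraindication is noticed only then, the trial loses a randomised participant for a reason that was on the medication record at screening. In a multicentre trial, sites may also resolve the conflict differently.

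**Working it through.** No sample size, power or error rate depends on this point, so the check is a comparison of texts followed by worked cases.

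**1. The two rules side by side**

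| | Exclusion 12 | Section 4.20.3 |
|---|---|---|
| Drugs | Photodynamic (light-activated) agents | Drugs sensitive to heat or light; open-ended; certain steroids as an example |
| Window | 14 days before enrollment | None stated; worded for patients who are taking the drug |
| Effect | Not eligible | Light not to be applied |
| Used in the 4.9.1 eligibility decision | Yes | No |

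**2. Timing.** Treatment runs 6 weeks at 3 sessions a week: 6 × 3 = 18 sessions over 6 × 7 = 42 days. Exclusion 12 looks back from enrollment and says nothing about drugs started later. Section 4.5.1 counts anyone who signs consent as enrolled, so exclusion 12 is also silent on a drug started between consent and visit 1. Section 4.20.3, having no window, applies throughout.

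**3. Cases**

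- *Photodynamic agent 10 days before enrollment.* Exclusion 12 applies and the person does not enter. No conflict.
- *One of the steroids meant by 4.20.3, taken at screening.* No exclusion applies. If the other criteria are met, the person is eligible under 4.9.1 and can be randomised. At visit 1, 4.20.3 says not to apply the light.
- *A 4.20.3 drug started in week 3.* Exclusion 12 is silent and 4.20.3 forbids further sessions. Use of such a drug is not among the specific withdrawal reasons in 4.19.1.

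**4. What the site can do in the last two cases**

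- Continue sessions: this departs from 4.20.3.
- Withhold sessions: while the drug continues, the week's three sessions cannot be completed, and 4.19.1 and 4.19.2 lead to withdrawal. If this happens at visit 1, the participant also has none of the three sessions that section 4.7 requires for analyzable data.

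**5. Is there a link that resolves it?** The medication form is completed at screening and at every visit (4.10 and the Table of Assessments), and before the laser at treatment visits (4.9.2). The information is therefore available in time. No passage says that an entry on the form is to be checked against 4.20.3, or what follows if it matches. The only pre-session check that the text connects with contraindication is the skin inspection.

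**6. Size.** One participant lost is 1/28 = 3.6% of an arm. The documents give no proportion of participants on such drugs, so no total follows.

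**The case against.** The strongest reply is that the protocol already forbids the harm. Section 4.20.3 says not to apply the light, has no time limit and so covers all 18 sessions, and 6.7 requires all personnel to read and follow the protocol. Treating such a person would be a deviation. This stands: a reader might infer that contraindicated participants will be treated under the plan, but the text does not direct that. What remains is that they can be randomised.

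Other points also stand in part:

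- A reader of 4.9.2 might infer that only the skin is checked before a session. The same section has the medication form completed first, so drug exposure is seen. Only the link to a decision is absent.
- A reader might take the opening of 4.20.3 as a flat contradiction of the list below it. It more naturally reports past experience with the device, with contraindications following under their own label. It is unclear under a heading about prohibited interventions, but it does not say that no drug is contraindicated.
- The drug bullet is garbled, perhaps by translation or text extraction, and the other items (abdominal points in pregnancy, children's epiphyseal lines, the thoracic region, the thyroid) look like general device labelling. The exact drug scope cannot be settled from this text. The prohibition and the steroid example are nevertheless legible, and neither is in the entry criteria.
- Reason 5 in 4.19.1 lets the investigator withdraw anyone. That permits a solution after randomisation; it does not prevent the problem at entry.
- Section 6.4 stops treatment for erythema or lasting discomfort because of unknown photosensitivity. It is not offered as the safeguard for a known drug, and should not be criticised as one.

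**Conclusion.** The inconsistency is real and should be corrected. Two drug rules with different scope and timing govern the same exposure, and eligibility rests on the narrower one. A person taking a 4.20.3 drug that is not a photodynamic agent can be eligible and randomised while contraindicated. Following the text then means either irradiation against 4.20.3 or loss of a randomised participant for a reason knowable at screening.

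This rests on reading the broken bullet as one sentence that covers drugs sensitive to heat or light and includes certain steroids. Its precise scope is uncertain.

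The size cannot be stated beyond 3.6% of an arm per participant lost. A reader might go further and infer biased tolerability results or excess dropout in the active arms, because sham emits 0 mW/cm² (section 3.2). It is true that a light–drug reaction could arise only where light is emitted. But the documents give no frequency of such drugs, no reaction rate and no discontinuation rate. Withholding sessions could remove a participant from any arm, sham included, and the sample size in 5.3 already allows for 20% loss. No quantified effect on the comparison is supported.

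**What to change.** Amend the protocol so that entry and treatment follow the same drug rule:

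- Reconcile exclusion 12 with the drug contraindication in 4.20.3, in both drugs covered and time window.
- State how the concomitant medication form, already completed at screening and before each session, is used with that rule.
- Rewrite the broken bullet in 4.20.3 so that the drug class is legible, and clarify whether the opening sentence reports past experience or states that nothing is prohibited.

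Which drugs count and what window applies are clinical decisions for the sponsor and the investigators; this review proposes neither.

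The cost is a short amendment, with the ethics committee approval that 6.1 requires, and no new form or visit. The downside is that a few otherwise eligible people may be excluded.

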5.1 General Considerations

It is expected that multiple sites, randomized, sham-controlled, double-blinded, double-blinded trials will include 112 patients, randomized into four groups. Each group will receive a different dose of NIR-TLT. Group tasks and dosing will be blinded to doctors, patients and outcome assessors. Device operators will be aware of the group assignments.

The purpose of this study is to compare the antidepressant effect of four different doses of NIR-TLT and to correlate this effect with the effects of the individual dose on brain electrophysiology and mitochondrial function.

5.2 Aims of the Study

Primary Aims:

A. To compare the effect(s) of each of the four doses of NIR-TLT on depression symptomatology: antidepressant effect.

Hypothesis 1: Total HAM-D 17 scores will vary in a NIR-TLT dose-dependent manner, with BPW dose being more effective.

We also expect to be able to estimate the effect size of the antidepressant action as a function of the irradiance applied to the NIR-TLT skin, with the BPW dose being more effective.

B. Compare the safety and tolerability of each dose.

Hypothesis 2: The doses of NIR-TLT tested in this study will be safe and well tolerated by patients with MDD, as assessed by SAFTEE-SI and serious adverse events.

We do not anticipate dose-dependent differences in reported side effects.

Secondary Aims:

C. To compare the effect(s) of each of the four doses of NIR-TLT on brain electrophysiology.

D. To compare the effect(s) of each of the four doses of NIR-TLT on mitochondrial function.

Transcranial Near Infrared Laser Therapy in Subjects with Major Depressive Disorder: A Laser Dosing Study.

E. To study the correlations (correlating) antidepressant effects, brain electrophysiology and mitochondrial function of each of the NIR-TLT doses.

5.3 Sample Size

The sample size was determined using G Power software version 3.1, considering a calculation by double mean difference with common standard deviation, assuming a significance level of 0.05 and 90% power. The parameters used were obtained from page 7 (section "Antidepressant effect according to clinician-rated measurement") of the previous ELATED-2 study (Cassano et al., 2018), where the mean difference of the HAM-D17 score for the experimental group was -10.8 ± 7.55 and for the control group 4.4 ± 6.65 ; such data identify a double difference of 6.4 with common standard deviation of 7.091. With this information, a total sample of 112 participants is obtained, taking into consideration a 20% loss rate. Each group will have 28 participants.

With $n=112$, in 4 groups in a longitudinal design, we estimated a power of 90% to differentiate ($\alpha=0.05$) the therapeutic effect of the dose, giving an antidepressant effect and an effect variance equivalent to that obtained in participants who completed the ELATED-2 study for all groups (Cassano et al., 2018b)

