4.5 Study Population

4.5.1 Population Description

The subject population for this study will consist of 112 randomized subjects between the ages of 18 and 75 years, of any ethnicity and diagnosed with MDD. The subject will meet all inclusion criteria, will have none of the exclusion criteria, and will provide written informed consent to participate in this clinical trial. Any subject who signs an informed consent will be considered enrolled in the study, although they will not be able to participate if they are not eligible for the study. In the event that a subject's ability to understand and communicate is compromised (as assessed by the investigator), local regulations regarding informed consent signatures must be followed.

Subjects will be recruited, through selections, advertisements and publications. Study participants will also be recruited through advertisements on the Internet, study center websites, etc. According to the strategies proposed by each researcher.

Participants who contact the respective study site staff in response to any of the announcements will complete the telephone screening to determine tentative eligibility for the study.

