4.7 Sample Size

The study is expected to include 112 subjects with analyzable data (at least 3 sessions - 1 week, after randomization).

Near Infrared Transcranial Laser Therapy in Subjects with Major Depressive Disorder: A study of Dosing with Laser.

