5.5 Efficacy and Safety Analysis for the Aims

It will be carried out as follows:

A. Antidepressant effect of NIR-TLT doses:

To compare the antidepressant effects of NIR-TLT doses, mean changes in HAM-D 17 scores (for evaluation of the Primary Assessment Criteria) and QIDS-C and CGI-S (for evaluation of the Secondary Assessment Criteria), will be performed for each dose at 3 time points (visit 1, visit 9 and visit 18) will be compared using a repeated measures ANCOVA. A significant ANCOVA interaction in mean score changes between groups will be taken as indicating that the groups have different antidepressant efficacy. If significant ANCOVA interactions are found, paired samples t-tests will be used to explore differences between scores/groups.

Both the full analysis and the analysis by intention will be performed to analyze the severity of depression at the endpoint. Patient attrition and dropout will be analyzed. The possible

Transcranial Near Infrared Laser Therapy in Subjects with Major Depressive Disorder: A Laser Dosing Study.

differences between treatment groups in dropouts will be examined with Fisher's exact test.

B. Brain electrophysiological effect of NIR-TLT doses:

To compare the effects of NIR-TLT doses on brain electrophysiology, changes in EEG spectral power in all spectral bands for each dose at 3 time points (visit 1, visit 9, and visit 18) will be compared using a repeated measures ANCOVA. A significant ANCOVA interaction in mean score changes between groups will be taken as indicating that the groups have different effects. If significant ANCOVA interactions are found, paired samples t-tests will be used to explore differences between groups.

C. Safety and tolerability of NIR-TLT doses:

To compare the safety and tolerability of NIR-TLT doses, mean changes iSAFTEE-SI scores at 3 time points (visit 1, visit 9, and visit 18) will be compared using a repeated measures ANOVA. A significant ANOVA interaction in mean score changes between groups will be taken as indicating that the NIR-TLT doses have different tolerability. If significant ANOVA interactions are found, paired samples t-tests will be used to explore differences between groups.

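### The 90% power for 112 participants follows from section 5.3's inputs only as an undeclared one-sided two-group t-test; two-sided it is about 83% with 22 evaluable per arm, and it is not power for the planned four-group analysis

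*Protocol*

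**What the plan says.** Section 5.3 describes a G*Power calculation for a difference between two mean changes with a common SD, at a significance level of 0.05 and 90% power. It does not say whether the test is one- or two-sided. The inputs come from ELATED-2: the HAM-D17 change "for the experimental group was -10.8 ± 7.55 and for the control group 4.4 ± 6.65", and "such data identify a double difference of 6.4 with common standard deviation of 7.091". The result is: "With this information, a total sample of 112 participants is obtained, taking into consideration a 20% loss rate. Each group will have 28 participants".

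The second paragraph of 5.3 restates the claim for the whole trial: "in 4 groups in a longitudinal design, we estimated a power of 90% to differentiate" the effect of dose at alpha 0.05, assuming an effect and "an effect variance equivalent to that obtained in participants who completed the ELATED-2 study for all groups".

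Section 5.5 plans a repeated-measures ANCOVA over visits 1, 9 and 18 in all four groups: "A significant ANCOVA interaction in mean score changes between groups will be taken as indicating that the groups have different antidepressant efficacy".

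On what 112 counts, section 4.5.1 says "The subject population for this study will consist of 112 randomized subjects". Section 1 and section 4.4 (28 per group) agree, and section 4.6 runs subject numbers to 150 only for losses before randomisation. Section 4.7 says "The study is expected to include 112 subjects with analyzable data".

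**The concern.** This is the protocol's only power statement. If the 90% depends on a one-sided test that nobody declared, the power under the usual two-sided reading is lower than printed. If it was computed for one pair of arms, it cannot also serve as the power of a four-group, non-directional interaction test. The reader cannot tell from 5.3 which contrast has 90% power, whether the 20% loss falls inside or on top of 112, or which ELATED-2 sample supplied the effect.

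**Working it through.** **Inputs (section 5.3):** difference 6.4; SD 7.091; alpha 0.05; power 90%; loss 20%; four equal groups. Standardised difference d = 6.4/7.091 = 0.9026. Power for n per arm comes from the noncentral t distribution with 2n − 2 df and noncentrality d·√(n/2).

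**1. Reproducing 112**

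| Test | Evaluable per arm for 90% | After 20% loss | Total |
|---|---|---|---|
| t-test, one-sided 0.05 | 22 (power 0.903; 21 gives 0.891) | 22/0.8 = 27.5 → 28 | **112** |
| t-test, two-sided 0.05 | 27 (power 0.902; 26 gives 0.891) | 27/0.8 = 33.75 → 34 | 136 |
| Four-group F test, three equal active effects | 25 (power 0.910; 24 gives 0.897) | 25/0.8 = 31.25 → 32 | 128 |

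Other two-sided variants also miss 112: inflating by ×1.2 gives 27 × 1.2 = 32.4 → 33, total 132; no loss gives 27 × 4 = 108. One other route reaches 28 per arm: the whole-sample SDs in section 3.1 (7.5 and 7.0, pooled 7.254), two-sided with no loss (power 0.900). That contradicts both the SD of 7.091 and the 20% loss stated in 5.3.

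**2. Two-sided power at the planned size, one active-sham pair.** Evaluable per arm after loss: 28 × 0.8 = 22.4, taken as 22.
- n = 22: noncentrality 0.9026 × √11 = 2.993, power 0.833.
- n = 28 (no loss): noncentrality 0.9026 × √14 = 3.377, power 0.913.

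**3. The planned four-group test.** Power for the interaction in 5.5 cannot be computed, because 5.3 gives no correlation between measurements and no pattern of group means. As an illustration only, take a simple four-group F test on change at visit 18, two-sided alpha 0.05, SD 7.091, with noncentrality n·Σ(mean − grand mean)²/SD². The patterns of means are assumptions.

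| Assumed effects (sham, BCW, BPW-1, BPW-2) | Σ(mean − grand mean)² | 22 per arm | 28 per arm |
|---|---|---|---|
| 0, 6.4, 6.4, 6.4 | 30.72 | 0.866 | 0.941 |
| 0, 3.2, 6.4, 6.4 | 28.16 | 0.832 | 0.919 |
| 0, 2.13, 4.27, 6.4 | 22.76 | 0.737 | 0.847 |

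Covariate adjustment could raise these. Using SD·√(1 − r²) and ignoring the lost degree of freedom, 90% at 22 per arm needs r of about 0.31 for the first pattern and just over 0.57 for the third.

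**4. Source of the effect**

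| ELATED-2 figures | Active | Sham | Difference |
|---|---|---|---|
| 5.3, used in the calculation | 10.8 | 4.4 | 6.4 |
| 3.1, 9 per group | 11.7 | 5.3 | 6.4 |
| 3.1, completers (6 and 7) | 15.7 | 6.1 | 9.6 |

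The completers named in 5.3's second paragraph do not give 6.4. The 6.4 agrees with the larger sample in 3.1, but the group means match neither. The SD does not settle it: equal weighting gives √((7.55² + 6.65²)/2) = 7.114, while 7.091 is what pooling gives with group sizes of 10 and 11, √((9 × 7.55² + 10 × 6.65²)/19) = 7.091. Neither sample in 3.1 has those sizes. This is an inference; 5.3 states no group sizes.

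**5. Sign.** As printed, −10.8 − 4.4 = −15.2. The stated 6.4 needs −10.8 − (−4.4) = −6.4. A true difference of 15.2 would need only 5 per arm one-sided (power 0.925) or 6 two-sided (0.916), so 15.2 was not used.

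**6. What 112 counts.** If 112 are randomised and 20% are lost, about 112 × 0.8 = 89.6 remain. Section 4.7's 112 analysable cannot hold together with 5.3. The choice matters: two-sided pair power is 83% on one reading and 91% on the other.

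**The case against.** The arithmetic behind 112 is not wrong: it reproduces exactly once a one-sided test is assumed, and 5.3 does name an experimental and a control group. Hypothesis 1 is directional, and the sidedness of the final test can be left to a statistical analysis plan. The 83% also assumes that lost participants contribute nothing, whereas 5.5 includes an analysis by intention, 4.19.1 schedules a HAM-D17 at the exit visit where possible, and 4.7 counts anyone with at least one week (three sessions) as analysable. With all 28 per arm analysed, two-sided power is 91% and the claim holds. Covariate adjustment would help further. The missing minus sign is resolved by the 6.4 in the same sentence, and a true completer effect of 9.6 would make the trial better powered, not worse.

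Much of this stands. The sign and the completer reference are minor corrections, the graded patterns of means are assumptions rather than evidence of a shortfall, and 91% is a fair figure if nobody is lost. But a directional hypothesis does not declare a one-sided test, and the test in 5.5 is non-directional. Section 5.3 itself builds in the 20% loss, so it cannot rely on full data for its 90%. Nor does any of this supply the inputs for the four-group longitudinal claim.

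**Conclusion.** The concern holds. With the inputs and loss rate in 5.3, 90% is the power of a one-sided t-test of one active arm against sham. Two-sided, that comparison has about 83% power with 22 evaluable per arm and about 91% with 28, unadjusted for covariates or for multiple comparisons. Reaching 90% two-sided under 20% loss would take 34 randomised per arm, 136 in total. The 90% claimed for the four-group longitudinal analysis is unsupported rather than shown to be false: it depends on a correlation and a pattern of means that 5.3 does not give. The count in 4.7, the completer attribution and the control sign each contradict other text in the protocol. The calculation also says nothing about differences between active doses, although Hypothesis 1 expects BPW to be the more effective.

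**What to change.** Keep 112 and amend the wording.

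- **5.3, test and comparison:** declare the test two-sided and name the comparison powered. Suggested text: 28 randomised per arm; about 22 evaluable after 20% loss gives about 83% power (two-sided 0.05) for one active-versus-sham difference of 6.4 with SD 7.091; about 91% if all 28 are analysed.
- **5.3, second paragraph:** drop the 90% for the four-group longitudinal design, or state the covariate or within-subject correlation and the pattern of means behind it.
- **5.3, scope:** say that the calculation covers an active-versus-sham difference and not differences between active doses.
- **5.3, source:** name the ELATED-2 analysis set and its group sizes, reconcile them with 3.1 and with the completer reference, and correct the control change to −4.4 after checking the source publication.
- **4.7:** align with 4.5.1 and 5.3, so that 112 is the number randomised.

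The cost is protocol wording in two sections: no extra patients and no change of analysis. The stated power becomes less favourable if 20% are lost.
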